3.4.4 Multiple Comparisons Procedures

The overall familywise error rate (FWER) will be controlled at $\alpha = 0.05$ using the sequential testing procedure for the primary efficacy endpoint comparing between the three dose levels of Ziltivekimab vs. placebo. The high dose (30 mg) will be compared with placebo at the beginning. If significant then the middle dose (15 mg) will be compared with placebo. If the middle dose is significant, then the low dose (7.5 mg) will be compared with placebo. The procedure stops whenever a nonsignificant test occurs.

3.4.5 Data Plots

Graphical data display for the efficacy parameters will be employed to present observed data and changes from baseline. The Ziltivekimab 7.5 mg, Ziltivekimab 15 mg, and Ziltivekimab 30 mg active dose groups as well the placebo group will be superimposed for visual comparison.

3.5 Pharmacokinetic Analysis

Pharmacokinetic analysis will be described in a separate pharmacokinetic analysis plan.

3.6 Pharmacokinetic/Pharmacodynamic Assessment

PK-PD analysis will be described in a separate PK-PD analysis plan.

3.7 Safety Assessment

Safety data will be summarized by actual treatment received (and in total for selected analyses) based on the Safety analysis population.

3.7.1 Adverse Events (AEs)

AEs will be captured from the date of informed consent through study completion. All AEs will be coded to system organ class and preferred term using MedDRA version 21.0.

Treatment-emergent adverse events (TEAEs) are defined as AEs that initiated or worsened on or after the date of first dose of study drug up to the end of safety-follow-up. For AEs occurring on the first dosing day, if the start time cannot be ascertained, the event will be counted as treatment-emergent. These events will be identified in the data by coded terms.

Adverse events of special interest (Section [2.3.4](#)) will be summarized by dose group and treatment assignment.

An overview of AEs will be provided including counts and percentages of subjects with the following:

- Any TEAEs (overall and by maximum severity)
- Any study drug related TEAEs (overall and by maximum severity)
- Any TEAEs of special interest (overall and by maximum severity)
- Any serious AEs (SAEs)

- Any treatment-emergent serious AEs (TESAEs)
- Any TEAEs leading to discontinuation of study drug
- Any TEAEs leading to discontinuation of study
- Any AEs leading to death
- Any severe hematologic AEs
- Any severe non-hematologic AEs

The number and percentage of patients reporting TEAEs and SAEs for each preferred term will be tabulated by system organ class, by system organ class and severity, and by system organ class and relationship to Study Drug. If more than one event occurred with the same preferred term for the same patient, the patient will be counted only once for that preferred term using the most severe or related occurrence for the summary by severity, or relationship to study drug, respectively.

Listings will be presented specifically for SAEs and TEAEs leading to discontinuation of study drug.

3.7.2 Clinical Laboratory Tests

Blood and urine samples for clinical laboratory tests will be collected and processed by a central laboratory.

Values and changes from baseline for lab parameters (excluding efficacy lab parameters) will be presented at each scheduled visit and baseline by laboratory test. The incidence of abnormalities (as defined by normal ranges) prior to the first dose of study drug and after the first dose of study drug will be summarized with counts and percentages of subjects.

All laboratory measurements will be listed.

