- To evaluate the effects of three dose levels of Ziltivekimab compared to placebo on Patient Reported Outcomes (PRO): Patient-Reported Outcomes Measurement Information System (PROMIS®) Fatigue 13a short form, selected items from the PROMIS fatigue item bank, the Optum 36-Item Short Form Survey (SF-36) v2® Health Survey, a Corvidia PRO, the PROMIS interest in sexual activity item, the Patient Global Impression of Change (PGIC), Patient Global Impression of Severity (PGIS), and the EuroQol-5D-5L (EQ-5D-5L).
- To evaluate the psychometric properties of the PROMIS Fatigue 13a short form and selected items from the PROMIS fatigue item bank, and the Corvidia electronic PRO (ePRO) items in CKD patients.
- To evaluate the effects of Ziltivekimab on systemic iron availability: transferrin saturation (TSAT), reticulocyte hemoglobin content (CHr), total iron binding capacity (TIBC), systemic iron stores (serum ferritin), serum iron, and systemic iron regulation (serum hepcidin).
- To evaluate the effects of Ziltivekimab compared to placebo on markers of cardiovascular risk (NT-pro-BNP) in patients with baseline NT-pro-BNP > 250 pg/mL.
- To evaluate the effects of Ziltivekimab compared to placebo on markers of anemia in patients with baseline hemoglobin < 11 g/dL.
- To evaluate the effects of Ziltivekimab compared to placebo on markers of inflammation malnutrition (i.e. albumin) in patients with baseline albumin < 4.0 g/dL.

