Chemistry ⁵	X	X	X	X	X	X	X	X	X	X	X	X	X	X	X	X
Spot urine protein-creatinine ratio		X							X							
Urinalysis (including albumin) ⁶			X						X			X	X			
Iron Indices ⁷	X		X						X			X	X	X	X	X
Serum Hepcidin			X						X				X			
TMPRSS6 Genotype test	X															

Table 1 SCHEDULE OF PROCEDURES

	Screening ¹		Treatment Period													Safety F/Up	
Visit Number	-2	-1	1	2	3	4	5	6	N/A	7	8	9	10	11/ET	12	13/ET	
Visit Day Window	-14	-7	1	8	22	29-35	43-49	57-63	78-84	85-91	113-119	141-147	155-161	162-168	190-196	218-224	
Visit Window	±2	±2	±2														
Visit Week	-2	-1	1	2	4	5	7	9	12	13	17	21	23	24/ET	28	32/ET	
Infectious Disease Screen ⁸		X															
Special RBCs ⁹			X								X				X	X	X
IL-6 ¹⁰				X	X	X			X		X	X	X	X	X	X	X
hs-CRP ¹¹	X		X	X	X			X		X	X	X	X	X	X	X	X
Serum Pregnancy, FSH ₁₂		X															
Ziltivekimab trough PK ¹³			X	X	X	X	X	X		X	X	X	X	X	X	X	X
ADA ¹⁴			X	X	X	X	X	X		X	X	X	X	X	X	X	X
12-lead ECG ¹⁵	X															X	
CKD Biomarkers ¹⁶		X	X								X			X	X		
NT-pro-BNP		X	X								X			X	X		
Lp(a), ApoB, ApoA1 ⁴	X	X						X		X			X	X			
Lipid Profile by NMR spectroscopy (fasting 8 hours) ⁴			X							X			X	X			
Cardiac Risk Biomarker ¹⁷			X								X				X		
Storage samples for Exploratory Biomarkers and RNA Testing ¹⁸	X										X				X		
DNA Testing (Stored Blood Samples)	X																
Limited Physical Examination ¹⁹		X													X		
INR ²⁰			X	X	X	X	X	X		X	X	X	X	X	X		
Adverse Events			X	X	X	X	X	X		X	X	X	X	X	X	X	X
PROMIS® 13a and Fatigue Items ²¹			X			X					X			X	X		
PROMIS® Sexual Interest Items ²¹			X			X					X				X		
CARES (Corvidia ePRO) ²²	X			X						X				X	X		
PGIS ²³	X			X						X					X		
PGIC ²⁴					X						X				X		
Optum SF-36 v2® ²⁵	X			X						X				X	X		
EQ-5D-5L ²⁶	X			X						X				X			

ET = Early Termination; F/Up = Follow-up.

1. If a Screening laboratory (excluding hematology) result is outside inclusion criteria parameters screening may be extended up to one week to allow for retesting of lab test(s) that did not meet inclusion criteria.
2. Vital signs include temperature, respiratory rate, heart rate, and blood pressure (patients may be re-evaluated within 2 weeks, at the discretion of the PI if anti-hypertensive therapy has been started or increased as a result of initial screening blood pressure). Whenever possible, vital signs will be obtained after at least 5 minutes resting in the supine position or, when necessary, in a semi-recumbent position. Vital signs will be done prior to ECG recordings.

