3. Hematology: hemoglobin, hematocrit, reticulocyte count, red blood count (RBC) indices (e.g., mean corpuscular volume (MCV), red cell distribution width (RDW), platelets, white blood count (WBC), WBC differential).
4. Lipids and subfractions (fasting 8 hours): total cholesterol, low density lipoprotein (LDL) cholesterol, high density lipoprotein (HDL), and triglycerides; Lp(a), ApoB, ApoA1.
5. Chemistry: sodium, potassium, chloride, bicarbonate (or CO₂), calcium, phosphate, alanine aminotransferase (ALT), aspartate aminotransferase (AST), blood urea nitrogen (BUN) creatinine, total bilirubin, direct bilirubin, alkaline phosphatase, albumin, glucose and eGFR calculated by CKD-EPI Creatinine Equation (<https://www.kidney.org/content/ckd-epi-creatinine-equation-2009>).
6. At Weeks 1 and 24, a portion of urine will be stored frozen for future analysis.
7. Iron Indices: TSAT, ferritin, total iron binding capacity (TIBC).
8. Infectious Disease Screen: HIV 1 and 2, Hepatitis B surface antigen, Hepatitis B surface antibody, Hepatitis C antibody, mycobacterium tuberculosis test (e.g., QuantiFERON) is preferred, but a purified protein derivative (PPD) skin test read within 48-72 hours by a qualified healthcare professional may also be performed (<https://www.cdc.gov/tb/publications/factsheets/testing/skintesting.htm>).
9. Special RBC: reticulocyte hemoglobin content (CHR).
10. IL-6: Interleukin-6. Pre-dose sampling.
11. hs-CRP: high-sensitivity C-reactive protein. Not using an average for inclusion, therefore test can be repeated as needed prior to randomization visit. Results after screening will be blinded.
12. Pregnancy: β -hCG; FSH: Follicle Stimulating Hormone.
13. On dosing Weeks 1, 5, 9, 13, 17, and 21, trough PK samples to be collected within -0.5 h pre-dose. Single PK blood samples will also be collected on Weeks 2, 4, 7, 23, 24/ET, 28, and 32/ET around the same time as the pre-dose samples were collected on previous dosing visits.
14. On dosing weeks 1, 5, 9, 13, 17, and 21, ADA: Anti-drug antibodies specimens to be collected within 0.5 h pre-dose.
15. Standard 12-lead ECG will be recorded in the supine position (or with the patient as flat as possible) after vital signs assessments. The ECG will be locally read by the Investigator.
16. Chronic Kidney Disease (CKD) Biomarkers: cystatin C and UACR.
17. Cardiac Risk marker: SSA, fibrinogen, and ST2.

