3.7.3 Vital Signs

Vital signs and change from baseline in vital signs will be summarized descriptively at each visit by treatment group. The number and percentage of patients with exceeding pre-defined absolute and relative threshold values will be summarized. These threshold values are presented in Table 2.

When calculating the percentages for the criterion related to a threshold, the numerator will be the number of subjects with normal baseline with respect to the specific criterion and at least 1 post-baseline outlier value within the analysis period; and the denominator will be the number of subjects with a baseline and at least 1 post-baseline assessment within the analysis period.

Table 2 Pre-defined Threshold Value for Vital Signs

Parameter	Criteria
Systolic Blood Pressure (SBP)	>25 mmHg increased or decreased from baseline
SBP	>160 mmHg
SBP	<90 mmHg
Heart Rate (HR)	>100 beats per minute
HR	<50 beats per minute
Respiration Rate	>24 breaths per minute

BMI	>10% increased from baseline
BMI	>10% decreased from baseline

All vital signs measurements will be listed.

3.7.4 *Electrocardiograms*

ECG interpretation (normal vs. abnormal) will be summarized using frequency and percentage at each visit by treatment group. ECG intervals (PR, QT, HR, and QTcF) will be summarized descriptively at each visit. The number and percentage of patients with exceeding pre-defined absolute and relative threshold values will be summarized. These threshold values are presented in Table 3.

When calculating the percentages for the criterion related to a threshold, the numerator will be the number of subjects with normal baseline with respect to the specific criterion and at least 1 post-baseline outlier value within the analysis period; and the denominator will be the number of subjects with a baseline and at least 1 post-baseline assessment within the analysis period.

Table 3 Pre-defined Threshold Value for ECG

Parameter	Criteria
PR Interval	>200 msec
QTcF	>450 msec
QTcF	>480 msec
QTcF	>500 msec
QTcF	Increase from baseline >30 msec
QTcF	Increase from baseline >60 msec

3.7.5 *Physical Examinations*

Physical examination clinically significant new or worsening findings will be reported as adverse events and will therefore be summarized as described for adverse events.

3.7.6 *Antibodies to Ziltivekimab*

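### Section 3.7.2 counts out-of-range laboratory values after first dose regardless of baseline, so for analytes often abnormal in stage 3-5 CKD the post-dose percentage mixes pre-existing with new abnormalities

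*SAP*

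**What the plan says.** Section 3.7.2 (Clinical Laboratory Tests) reports "The incidence of abnormalities (as defined by normal ranges) prior to the first dose of study drug and after the first dose of study drug" as counts and percentages of subjects. It does not restrict the post-dose numerator or denominator by baseline status, does not separate low from high, and plans no shift table. The section also gives values and changes from baseline by visit (efficacy laboratory parameters excepted) and full listings. The introduction to section 3.7 makes safety displays by actual treatment received.

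Neighbouring sections treat baseline differently:

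- For the vital-sign thresholds in 3.7.3, "the numerator will be the number of subjects with normal baseline with respect to the specific criterion" and a post-baseline outlier, while "the denominator will be the number of subjects with a baseline and at least 1 post-baseline assessment within the analysis period". The ECG-interval thresholds in 3.7.4 use the same rule.
- TEAEs in 3.7.1 are "AEs that initiated or worsened on or after the date of first dose of study drug".
- The overall ECG reading in 3.7.4 has no baseline condition: "ECG interpretation (normal vs. abnormal) will be summarized using frequency and percentage at each visit by treatment group".

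The SAP addendum, section 2.1, sets the safety baseline to the Day 1 value, or the last pre-dose evaluation if that is missing. It adds no condition to the laboratory count.

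**The concern.** The word incidence suggests abnormalities that arise on treatment. Read literally, the rule also counts abnormalities the patient brought into the trial.

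This matters only for analytes often abnormal at entry. The documents point to one group: an exploratory objective in 2.1.5 concerns effects "on markers of anemia in patients with baseline hemoglobin < 11 g/dL", and the hematology panel (Table 1, footnote 3) covers "hemoglobin, hematocrit, reticulocyte count, red blood count (RBC) indices". Low hematocrit or red cell count before dosing is therefore plausible in some patients, and neither is among the modelled endpoints in 3.4.3. BUN and phosphate are further candidates in stage 3-5 CKD, but that is an assumption.

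For such analytes the pre-dose percentage shows the baseline burden but not which patients became abnormal. The trial is meant to select a dose for a possible outcome trial (section 2.1), so a laboratory signal by dose should be readable from the table.

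**Working it through.** **Inputs.** The only relevant design figure is the arm size. Section 2.2.4 gives 54 per group and 10% dropout, and 54 / 0.90 = 60, as stated. The SAP gives no laboratory abnormality rates, so the rest are assumptions: new abnormality in a = 10% (placebo) and b = 25% (drug) of patients not abnormal at baseline; share p abnormal at baseline, varied; share s of those still abnormal after dosing, first 100%, then 80%, equal in both arms.

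**Three ways of counting.**

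- Planned (3.7.2): ps + (1 − p)a against ps + (1 − p)b, n = 60.
- Vital-sign rule (3.7.3): (1 − p)a against (1 − p)b, n = 60.
- At-risk count: a against b, n = 60(1 − p).

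**Ratio.** At p = 20% and s = 100% the planned table shows 0.20 + 0.80 × 0.10 = 28% and 0.20 + 0.80 × 0.25 = 40%, so 40 / 28 = 1.43. The other two counts give 25 / 10 = 2.50 at every p.

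**Difference.** The term ps cancels when s is the same in both arms. The planned table and the vital-sign rule then give the same difference, (1 − p) × 15 points. The at-risk difference is 15 points throughout.

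**Standard error of the difference.** SE = √[(P1(1 − P1) + P2(1 − P2)) / n]. Differences and SEs are in percentage points, with s = 100%.

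| p | Planned, placebo vs drug | Planned ratio | Difference (planned = vital-sign rule) | SE planned | SE vital-sign rule | SE at-risk (n per arm) |
|---|---|---|---|---|---|---|
| 0% | 10 vs 25% | 2.50 | 15 | 6.8 | 6.8 | 6.8 (60) |
| 2% | 11.8 vs 26.5% | 2.25 | 14.7 | 7.1 | 6.7 | 6.9 (59) |
| 20% | 28 vs 40% | 1.43 | 12 | 8.6 | 6.2 | 7.6 (48) |
| 40% | 46 vs 55% | 1.20 | 9 | 9.1 | 5.5 | 8.8 (36) |
| 60% | 64 vs 70% | 1.09 | 6 | 8.6 | 4.6 | 10.8 (24) |
| 80% | 82 vs 85% | 1.04 | 3 | 6.8 | 3.3 | 15.2 (12) |

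**Ability to see the effect (difference / SE)** at 20, 40, 60 and 80%:

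- Planned: 1.40, 0.99, 0.70, 0.44.
- Vital-sign rule: 1.92, 1.63, 1.30, 0.90.
- At-risk: 1.97, 1.71, 1.40, 0.99.

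**Sensitivity.**

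- With s = 80% the planned ratios at 20 to 80% are 1.50, 1.24, 1.12 and 1.05.
- With new rates of 2% and 8% (true ratio 4.0, s = 100%) the planned ratio is 0.264 / 0.216 = 1.22 at p = 20% and 0.448 / 0.412 = 1.09 at p = 40%.
- With new rates of 60% and 80%, p = 50% and s = 100%, the SE comparison with the vital-sign rule reverses: 6.5 points planned, 8.7 under the vital-sign rule. The condition that new rates lie below 50% is needed.
- If persistence differs by arm the direction is not assured. At p = 60% with s = 100% on placebo and 80% on drug, the table shows 64% against 0.48 + 0.10 = 58%, a ratio of 0.91.

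**The case against.** **Precision.** A reader might infer that the planned count is less precise. That is not so in general. Against an at-risk denominator it has the smaller SE at 60% abnormal at baseline (8.6 against 10.8 points) and at 80% (6.8 against 15.2). On the log-ratio scale, with 10% against 20% new and half abnormal at baseline, its SE is 0.157 against 0.683 under the vital-sign rule. What falls is the difference relative to its SE.

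**Benchmark.** The SAP plans percentages, not ratios or tests, and the absolute difference matches the SAP's own vital-sign rule. Percentages such as 28 against 40 are still visibly apart. This stands. The loss shows in the ratio and in the signal relative to noise.

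**Consistency.** The ECG reading is not conditioned on baseline either, so the SAP has no uniform rule to breach.

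**Coverage elsewhere.** Hemoglobin, including the subgroup below 11 g/dL, is analysed as an efficacy endpoint. TIMI categories (3.7.7) use falls in hemoglobin and hematocrit. Severe neutrophil and platelet events are summarized separately (2.3.5). Change-from-baseline tables, listings and TEAEs remain. These narrow the gap without closing it: mean changes can hide a minority who cross a limit, and listings do not summarize by arm.

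**Unseen documents.** Entry limits may cap baseline abnormality for chemistry; Table 1, footnote 1 provides that "If a Screening laboratory (excluding hematology) result is outside inclusion criteria parameters screening may be extended up to one week". The separate programming specifications (section 6) may also fix the layout. Both are fair cautions on size.

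**Conclusion.** The point holds in limited form. As written, 3.7.2 reports pre-existing abnormalities among its post-dose cases. For analytes often abnormal at baseline this pulls the drug-placebo ratio towards 1, provided baseline abnormalities persist similarly in both arms. Equal persistence is least secure for red cell measures, since an effect on anemia is itself a study objective. When new-abnormality rates are below 50%, a drug effect is also harder to see.

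The size rests wholly on assumed rates: a true ratio of 2.50 becomes 1.43 at 20% abnormal at baseline and 1.09 at 60%. It is nil at 0% and small at 2%, so for ALT, AST or bilirubin it may be negligible.

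A reader might go further and infer a biased absolute difference or a threat to the trial's conclusions. The documents support neither. With equal persistence the difference equals that of the vital-sign rule, the table is descriptive, and no efficacy result depends on it. This is a worthwhile, cheap improvement.

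**What to change.** Keep the planned pre-dose and post-dose counts in 3.7.2 and add two displays by treatment group.

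1. Separately for low and high, the number and percentage of patients newly abnormal in that direction after dosing. Denominator: patients not abnormal in that direction at the Day 1 safety baseline (last pre-dose value if missing) who have at least one post-dose value, with n shown per analyte.
2. A shift table per analyte from baseline to worst post-dose value (low, normal, high).

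The cost is a few lines of SAP wording and a standard program on data already collected. The downside is smaller denominators and wider intervals where baseline abnormality is common (12 per arm at 80%). The new count also misses worsening in patients already abnormal in that direction, which must be read from the change-from-baseline summaries and listings.

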3.7.3 Vital Signs

Vital signs and change from baseline in vital signs will be summarized descriptively at each visit by treatment group. The number and percentage of patients with exceeding pre-defined absolute and relative threshold values will be summarized. These threshold values are presented in Table 2.

When calculating the percentages for the criterion related to a threshold, the numerator will be the number of subjects with normal baseline with respect to the specific criterion and at least 1 post-baseline outlier value within the analysis period; and the denominator will be the number of subjects with a baseline and at least 1 post-baseline assessment within the analysis period.

Table 2 Pre-defined Threshold Value for Vital Signs

Parameter	Criteria
Systolic Blood Pressure (SBP)	>25 mmHg increased or decreased from baseline
SBP	>160 mmHg
SBP	<90 mmHg
Heart Rate (HR)	>100 beats per minute
HR	<50 beats per minute
Respiration Rate	>24 breaths per minute

BMI	>10% increased from baseline
BMI	>10% decreased from baseline

All vital signs measurements will be listed.

3.7.4 *Electrocardiograms*

ECG interpretation (normal vs. abnormal) will be summarized using frequency and percentage at each visit by treatment group. ECG intervals (PR, QT, HR, and QTcF) will be summarized descriptively at each visit. The number and percentage of patients with exceeding pre-defined absolute and relative threshold values will be summarized. These threshold values are presented in Table 3.

When calculating the percentages for the criterion related to a threshold, the numerator will be the number of subjects with normal baseline with respect to the specific criterion and at least 1 post-baseline outlier value within the analysis period; and the denominator will be the number of subjects with a baseline and at least 1 post-baseline assessment within the analysis period.

Table 3 Pre-defined Threshold Value for ECG

Parameter	Criteria
PR Interval	>200 msec
QTcF	>450 msec
QTcF	>480 msec
QTcF	>500 msec
QTcF	Increase from baseline >30 msec
QTcF	Increase from baseline >60 msec

3.7.5 *Physical Examinations*

Physical examination clinically significant new or worsening findings will be reported as adverse events and will therefore be summarized as described for adverse events.

3.7.6 *Antibodies to Ziltivekimab*

The immunogenic potential of Ziltivekimab will be assessed by summarizing the number and percentage of patients who develop detectable anti-drug antibodies (ADA). Anti-drug antibody titers will be summarized descriptively for ADA positive samples and the impact of ADA on PK will be assessed if data allows.

3.7.7 *Bleeding Events*

Bleeding events will be classified using the Thrombolysis In Myocardial Infarction (TIMI) Bleeding Classification

Table 4 TIMI Bleeding Classification

Parameter	Criteria
Major	Intracranial hemorrhage or a ≥ 5 g/dL decrease in the hemoglobin concentration or a $\geq 15\%$ absolute decrease in the hematocrit

Minor	Observed blood loss: ≥ 3 g/dL decrease in the hemoglobin concentration or $\geq 10\%$ decrease in the hematocrit. No observed blood loss: ≥ 4 g/dL decrease in the hemoglobin concentration or $\geq 12\%$ decrease in the hematocrit
Minimal	Any clinically overt sign of hemorrhage (including imaging) that is associated with a <3 g/dL decrease in the hemoglobin concentration or $<9\%$ decrease in the hematocrit
All TIMI definitions take into account blood transfusions, so that hemoglobin and hematocrit values are adjusted by 1 g/dL or 3%, respectively, for each unit of blood transfused. Therefore, the true change in hemoglobin or hematocrit if there has been an intervening transfusion between two blood measurements is calculated as follows: Δ Hemoglobin = [baseline Hgb – post-transfusion Hgb] + [number of transfused units]; Δ Hematocrit = [baseline Hct – post-transfusion Hct] + [number of transfused units \times 3].	

Tables will be generated for each of the TIMI Bleeding Classification parameters by treatment and in total. Bleeding events will also be listed.

3.7.8 Exploratory Analyses of Efficacy and Safety Endpoints Based on Baseline Hemoglobin (≥ 11 or <11 g/dL)

Exploratory analyses may be performed for the primary and secondary efficacy endpoints with a stratified analysis by baseline hemoglobin (≥ 11 g/dL or <11 g/dL) and CKD stage (3, 4 or 5).

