2. DATA ANALYSIS CHANGES

2.1 Definition of Baseline for Exploratory Efficacy Endpoints and Safety Endpoints

The SAP version 1.0 defines the baseline value for the primary efficacy endpoint hs-CRP, secondary efficacy endpoint Serum Amyloid A, and exploratory efficacy endpoints Hemoglobin, Serum Albumin, and NT-pro-BNP as the average of lab value at Day 1 and prior assessment(s). For the CARES Corvidia ePRO endpoint, baseline is defined as the average of 7 consecutive measurements (Day -7 to Day -1) prior to first dose initiation.

Similarly, baseline for all exploratory efficacy endpoints will be defined as follows:

- For endpoints where lab assessments were collected at multiple visits prior to the initiation of study drug, baseline will be calculated as average of all values prior to the first dose.
- For endpoints where lab assessments were collected at Day 1 only, baseline will be defined as the Day 1 value.

For all safety endpoints, baseline will be defined as the Day 1 value. If missing, the last evaluation prior to the initiation of the study drug will be considered the baseline.

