2.2.4 Sample Size Determination

Approximately 240 patients (60 per group) will be randomized.

The primary efficacy endpoint is percent change from baseline in hs-CRP (average of the hs-CRP value prior to randomization and Day 1) to Week 13 between each active group and placebo. Based on the observed treatment difference in percent change from baseline in hs-CRP of -60.74% between combined COR-001-01 active groups and placebo and the associated pooled SD of 16.893% in hs-CRP at Week 4 from the final analysis of study COR-001-SC1, a sample size of 54 per group yields more than 99% power with 2-sided alpha=0.05. Taking into consideration the dropout rate of 10% by the end of the study, a sample size of 60 per group is planned for this study.

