3.2 Analysis Populations

3.2.1 *Intent-to-Treat (ITT) Analysis Population*

The ITT analysis population includes all randomized patients and will be the primary population for analyses of disposition, baseline, and efficacy data.

3.2.2 *Per-Protocol (PP) Analysis Population*

The PP analysis population will be the secondary population for analyses of disposition, baseline data, and efficacy data. For PP analysis population, treatment classification will be based on the randomized treatment. PP analysis population is defined as all randomized patients who completed the study and did not incur a significant protocol violation. Significant protocol violations may include but are not limited to:

- Failed to meet eligibility criteria
- Took the wrong study drug (i.e., did not take the randomized study drug)
- Had study drug compliance <80%
- Took a restricted concomitant medication
- Failed to complete the primary efficacy assessment

A list of subjects with significant protocol violations leading to exclusion from PP analysis population will be finalized prior to unblinding the randomized treatment assignments.

3.2.3 *Safety Analysis Population*

The Safety analysis population is defined as all randomized patients who received at least one dose of study drug. All safety data will be analyzed using the Safety analysis population. For the Safety analysis population, treatment classification will be based on the actual treatment received.

3.2.4 *Pharmacokinetics (PK) Analysis Population*

The PK analysis population is defined as all randomized patients who received at least one dose of study drug and had at least one post-dose PK blood sample. For the PK analysis population, treatment classification will be based on the actual treatment received.

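### For the nine absolute thresholds, the vital-sign and ECG outlier percentages divide new outliers among patients at risk by all assessed patients

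*SAP*

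**What the plan says.** Clinical SAP 3.7.3 (Vital Signs) promises that "The number and percentage of patients with exceeding pre-defined absolute and relative threshold values will be summarized", and section 3.7.4 (Electrocardiograms) does the same for ECG. Both sections then give one identical rule for the percentage. For the top of the fraction, "the numerator will be the number of subjects with normal baseline with respect to the specific criterion and at least 1 post-baseline outlier value". For the bottom, "the denominator will be the number of subjects with a baseline and at least 1 post-baseline assessment within the analysis period". The condition of a "normal baseline with respect to the specific criterion" appears only in the numerator.

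The rule covers all 14 rows of Tables 2 and 3. Nine are absolute limits: SBP >160, SBP <90, HR >100, HR <50, respiration rate >24, PR >200, and QTcF >450, >480 and >500. Five are changes from baseline: SBP change >25 mmHg, BMI up >10%, BMI down >10%, and QTcF increase >30 and >60 msec.

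Section 2.1 of the SAP addendum settles which value is the baseline ("For all safety endpoints, baseline will be defined as the Day 1 value", or the last value before study drug if that is missing). It leaves the percentage rule as it stands. No other section restricts the denominator or adds a percentage among patients at risk.

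**The concern.** Two definitions would be coherent. One counts every patient with a post-baseline outlier over every patient assessed, which is the overall frequency. The other counts patients with a new outlier over patients who could have had a new one, which is the risk of a new abnormality. The SAP takes its numerator from the second and its denominator from the first. The result answers neither question directly.

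The tables are read across arms, in a trial that section 2.1 of the clinical SAP says is meant to choose a dose for a possible cardiovascular outcome trial, in patients with stage 3–5 CKD at high cardiovascular risk. A rate of new high blood pressure or prolonged QTcF that is diluted by patients who were never at risk can look reassuring for the wrong reason. Randomization is stratified by hemoglobin and CKD stage only, so baseline blood pressure and QTcF are balanced between arms only by chance. Two arms with the same underlying risk can therefore show different percentages.

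**Working it through.** The SAP states no outlier rate, so there is no figure of its own to reproduce. The check is algebraic, with illustrative values.

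**Inputs**
- Numerator and denominator rules: clinical SAP 3.7.3 and 3.7.4.
- N, patients in an arm with a baseline and a post-baseline value: 60 for illustration, from the planned arm size in section 2.2.4. The true N is smaller if any patient lacks either value.
- f, share of those N already beyond the threshold at baseline: not in the documents; assumed, 0% to 50%.
- r, new-outlier rate among patients not beyond the threshold at baseline: not in the documents; assumed, 20%.

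**Absolute thresholds**
- Patients at risk: N(1 − f). New outliers: N(1 − f)r.
- SAP percentage: N(1 − f)r / N = (1 − f)r.
- Percentage among patients at risk: N(1 − f)r / [N(1 − f)] = r.
- Ratio of the two: 1 − f.

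| Assumed f | At risk (of 60) | Expected new outliers | SAP percentage | Percentage at risk |
|---|---|---|---|---|
| 0% | 60 | 12.0 | 20.0% | 20.0% |
| 10% | 54 | 10.8 | 18.0% | 20.0% |
| 20% | 48 | 9.6 | 16.0% | 20.0% |
| 30% | 42 | 8.4 | 14.0% | 20.0% |
| 50% | 30 | 6.0 | 10.0% | 20.0% |

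**Comparison of two arms.** Take r = 20% in both arms, with f = 20% in one and 35% in the other. The SAP rule gives 0.20 × 0.80 = 16.0% and 0.20 × 0.65 = 13.0%, a difference of 3.0 points where the risks are equal.

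How unusual is that imbalance? At 60 per arm and an average f of 27.5%, the standard error of the difference in f is √(2 × 0.275 × 0.725 / 60) ≈ 8.2 points. A gap of 15 points is about 1.8 standard errors, so it lies toward the edge of what chance produces. The sampling standard error of the two printed rates is √(0.16 × 0.84 / 60 + 0.13 × 0.87 / 60) ≈ 6.4 points, so the 3.0-point distortion is well inside ordinary noise at this sample size.

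**Change criteria.** At baseline the change from baseline is zero, so no patient can already meet SBP change >25, BMI change >10% or QTcF increase >30 or >60. Hence f = 0, (1 − f)r = r, and these rows are not understated.

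**The case against.** The strongest reply is that nothing here is miscalculated. The numerator is a subset of the denominator, so the percentage is a valid proportion: patients with a new outlier among all patients assessed. The SAP does not call these outliers treatment-emergent, so the rate among patients at risk is not the only possible target. That is fair as far as it goes. The defect is a poorly matched denominator, not an arithmetic slip. But a numerator that excludes patients abnormal at baseline is naturally read as a risk of new abnormality, and this denominator does not deliver one.

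The second reply concerns consequence. The tables are descriptive, and the SAP ties no test, stopping rule or efficacy endpoint to them. Visit-wise summaries of vital signs and ECG intervals stand beside them, the count of patients is printed next to the percentage and does not depend on the denominator, and subject listings and analysis datasets allow the at-risk rate to be recomputed. This stands, and it lowers the severity. One qualification: under section 4.1, the sponsor team that receives the Week 13 results gets no subject-level data, so those readers could not rebuild the denominator at that point.

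A reader might also infer that every vital-sign and ECG outlier percentage is biased downward. The documents do not support that: five of the 14 rows are change criteria with f = 0. Nor do they support a typical understatement of 10% to 40%. They give no baseline share for any criterion, and nothing in them sets a floor of 10% for rows such as SBP <90 or QTcF >500, where f may be near zero.

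**Conclusion.** The mismatch is real and is stated identically in sections 3.7.3 and 3.7.4. For the nine absolute thresholds, the reported percentage equals the rate among patients at risk times (1 − f). It is understated whenever some patients are already beyond the threshold and new outliers occur among the rest, and it can create an apparent difference between arms when f differs.

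The size cannot be fixed from the documents. The relative understatement equals f itself: none at f = 0, 20% at an assumed f = 20%, 50% at an assumed f = 50%. It is probably small for criteria rarely met at baseline. For the five change criteria the percentage is sound and only the wording is unclear, since nobody can be abnormal at baseline with respect to a change from baseline.

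Severity is moderate to minor. A reader might take this as a flaw that must be corrected before the safety results can be used. The descriptive role of the tables and the counts and listings beside them do not support that, and the efficacy analyses are untouched.

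**What to change.** In both sections, replace the single rule with two:

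- **Absolute thresholds:** numerator and denominator are both limited to patients who do not meet that criterion at baseline and have at least one post-baseline value in the analysis period. Each criterion has its own denominator, so QTcF >450, >480 and >500 are handled separately.
- **Change-from-baseline criteria:** numerator and denominator both use all patients with a baseline and at least one post-baseline value, with no normal-baseline condition.

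Print each row as n/N (%), so that the denominator is visible. The cost is two sentences of SAP text and a small change to the table program. The downside is that the denominator will vary from row to row and between arms, which the n/N layout makes plain.
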